### 8.3 Dose Modifications for Pembrolizumab

Adverse events (both non-serious and serious) associated with pembrolizumab exposure may represent an immunologic etiology. These AEs may occur shortly after the first dose or several months after the last dose of treatment. Pembrolizumab must be withheld for drug-related toxicities and severe or life-threatening AEs as per the Table below. See [Section 9.0](#) for supportive care guidelines, including use of corticosteroids.

Table 8.31 Dose Modification Guidelines for Drug-Related Adverse Events for Pembrolizumab

CTCAE System/Organ/Class (SOC)	Adverse Event	Hold Treatment for Grade	Timing for Restarting Treatment	Treatment Discontinuation
Gastrointestinal disorders	Diarrhea or Colitis	2-3	AE resolves to Grade 0-1	AE does not resolve within 12 weeks of last dose or inability to reduce corticosteroid to 10mg or less of prednisone or equivalent per day within 12 weeks
		4	Permanently discontinue	Permanently discontinue
Investigations	AST, or ALT, or Blood bilirubin increased	2	AE resolves to Grade 0-1	AE does not resolve within 12 weeks of last dose.
		3-4	Permanently discontinue (see exception below) a	Permanently discontinue
Metabolism and nutrition disorders	Glucose intolerance (Type 1 diabetes mellitus [if new onset]) or Hyperglycemia	T1DM or 3-4	Hold pembrolizumab for new onset Type 1 diabetes mellitus or Grade 3-4 hyperglycemia associated with evidence of beta cell failure	Resume pembrolizumab when patients are clinically and metabolically stable.
Endocrine disorders	Endocrine disorders – Other, specify: Hypophysitis	2-4	AE resolves to Grade 0-1. Therapy with pembrolizumab can be continued while endocrine replacement therapy is instituted	AE does not resolve within 12 weeks of last dose or inability to reduce corticosteroid to 10 mg or less of prednisone or equivalent per day within 12 weeks
Endocrine disorders	Hyperthyroidism	3	AE resolves to Grade 0-1	AE does not resolve within 12 weeks of last dose or inability to reduce corticosteroid to 10 mg or less of prednisone or equivalent per day within 12 weeks
		4	Permanently discontinue	Permanently discontinue
Endocrine disorders	Hypothyroidism		Therapy with pembrolizumab can be continued while thyroid replacement therapy is instituted	Therapy with pembrolizumab can be continued while thyroid replacement therapy is instituted

CTCAE System/Organ/Class (SOC)	Adverse Event	Hold Treatment for Grade	Timing for Restarting Treatment	Treatment Discontinuation
General disorders and administration site conditions	Infusion related reaction	2 b	AE resolves to Grade 0-1	Permanently discontinue if AE develops despite adequate premedication
		3-4	Permanently discontinue	Permanently discontinue
Respiratory, thoracic and mediastinal disorders	Pneumonitis	2	AE resolves to Grade 0-1	AE does not resolve within 12 weeks of last dose or inability to reduce corticosteroid to 10 mg or less of prednisone or equivalent per day within 12 weeks
		3-4	Permanently discontinue	Permanently discontinue
Renal and urinary disorders	Acute kidney injury or Chronic kidney disease (e.g Renal failure or Nephritis)	2	AE resolves to Grade 0-1	AE does not resolve within 12 weeks of last dose or inability to reduce corticosteroid to 10 mg or less of prednisone or equivalent per day within 12 weeks
		3-4	Permanently discontinue	Permanently discontinue
	All Other Drug-Related Adverse Events c	3 or severe	AE resolves to Grade 0-1	AE does not resolve within 12 weeks of last dose or inability to reduce corticosteroid to 10 mg or less of prednisone or equivalent per day within 12 weeks
		4	Permanently discontinue	Permanently discontinue

**Note: Permanently discontinue for any severe or Grade 3 drug-related AE that recurs or any life-threatening event.**

a For patients with liver metastasis who begin treatment with Grade 2 AST or ALT, if AST or ALT increases by greater than or equal to 50% relative to baseline and lasts for at least 1 week then patients should be discontinued.

b If symptoms resolve within one hour of stopping drug infusion, the infusion may be restarted at 50% of the original infusion rate (e.g., from 100 mL/hr to 50 mL/hr). Otherwise dosing will be held until symptoms resolve and the subject should be premedicated for the next scheduled dose.

c Patients with intolerable or persistent Grade 2 drug-related AE may hold study medication at physician discretion. Permanently discontinue study drug for persistent Grade 2 adverse reactions for which treatment with study drug has been held, that do not recover to Grade 0-1 within 12 weeks of the last dose.

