### 8.32 Other instructions for pembrolizumab

If pembrolizumab-related toxicity does not resolve to Grade 0-1 within 12 weeks after last administration of study drug, study therapy discontinuation is recommended. With Investigator agreement, patients with a laboratory adverse event still at Grade 2 may continue in the study only if asymptomatic and controlled.

In patients who continue on study therapy after experiencing an Adverse Event warranting potential dose modification, if considered drug-related by the investigator, once the patient has recovered to Grade 0-1 the dosing interval in

subsequent cycles will be increased by 1 week (e.g., to 3 weeks in patients who were on an every 2-week schedule). Following each such dose delay due to toxicity, the dosing interval should increase by an additional week. For example, patients who began the study on a 3-week dosing schedule, and have stopped drug twice for due to a drug-related toxicity that meets the above criteria, should now be dosing every 5 weeks.

For patients who experience a recurrence of the same severe AEs listed above with rechallenge of pembrolizumab, a consultation with the Investigator will occur to determine whether the patient should continue in the study. A patient who experiences the same SAE of the same NCI CTCAE grade or higher with rechallenge of pembrolizumab must discontinue pembrolizumab immediately.

Reduced dose of pembrolizumab dose (ie, below 200 mg) will not be administered.

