### 10.1 Adverse Event Characteristics

**CTCAE term (AE description) and grade:** The descriptions and grading scales found in the revised NCI Common Terminology Criteria for Adverse Events (CTCAE) version 4.0 will be utilized for AE reporting. All appropriate treatment areas should have access to a copy of the CTCAE version 4.0. A copy of the CTCAE version 4.0 can be downloaded from the CTEP web site:

([http://ctep.cancer.gov/protocolDevelopment/electronic\\_applications/ctc.htm](http://ctep.cancer.gov/protocolDevelopment/electronic_applications/ctc.htm))

- a. Identify the grade and severity of the event using the CTCAE version 4.0.
- b. Determine whether the event is expected or unexpected (see Section 10.2).
- c. Determine if the adverse event is related to the study intervention (agent, treatment or procedure) (see Section 10.3).
- d. Determine whether the event must be reported as an expedited report. If yes, determine the timeframe/mechanism (see Section 10.4).
- e. Determine if other reporting is required (see Section 10.5).
- f. Note: All AEs reported via expedited mechanisms must also be reported via the routine data reporting mechanisms defined by the protocol (see Sections 10.6 and 18.0).

NOTE: A severe AE is NOT the same as a serious AE, which is defined in Section 10.4.

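### Table 8.31 and Section 8.32 give conflicting instructions on stopping pembrolizumab after certain recurrent severe events and after certain Grade 2 laboratory events unresolved at 12 weeks

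*Combined protocol and SAP*

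**What the plan says.** **Recurrence.** The note under Table 8.31 (Section 8.3) is unconditional: "Permanently discontinue for any severe or Grade 3 drug-related AE that recurs or any life-threatening event". Section 8.32 takes up recurrence of the same severe event when pembrolizumab is given again, and says that "a consultation with the Investigator will occur to determine whether the patient should continue in the study". It then adds one mandatory case: "A patient who experiences the same SAE of the same NCI CTCAE grade or higher with rechallenge of pembrolizumab must discontinue pembrolizumab immediately".

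**Twelve weeks.** In the Grade 2 row for AST, ALT or bilirubin, the discontinuation column of Table 8.31 reads "AE does not resolve within 12 weeks of last dose". Footnote c, attached to the row for all other drug-related events, says "Permanently discontinue study drug for persistent Grade 2 adverse reactions for which treatment with study drug has been held", limited to reactions "that do not recover to Grade 0-1 within 12 weeks of the last dose". Section 8.32 restates the 12-week limit for pembrolizumab toxicity in general but only recommends stopping. It then provides that, if the Investigator agrees, "patients with a laboratory adverse event still at Grade 2 may continue in the study only if asymptomatic and controlled".

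**How binding the rules are.** The opening of Section 8.0 asks for strict adherence during the first two cycles and treats the modifications as guidance after that. It also defines discontinuation as a complete stop of treatment.

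**The concern.** The table and the section that follows it give different answers to the same clinical question, and neither refers to the other. A site working from the table would stop a patient whom a site working from Section 8.32 could continue.

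The decision at issue is re-exposure to, or continuation of, a checkpoint inhibitor after a severe or unresolved event, so the first stake is patient safety. The second is consistency of the data. Uneven stopping changes pembrolizumab exposure, and through it could change the safety summary and who is still on the combination when response is assessed. Section 8.1 names diarrhea and liver function abnormalities as events attributable to either drug. Both are within reach of the conflicts: diarrhea through recurrence, liver tests through the 12-week limit.

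**Working it through.** The plan states no figure on this point, so the check is a comparison of the texts case by case.

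**Step 1: where can a recurrence on rechallenge arise?** Table 8.31 permits restarting after a Grade 3 event for diarrhea/colitis, hyperglycemia, hypophysitis, hyperthyroidism and the row for all other drug-related events. Grade 3 liver, infusion-reaction, pneumonitis and kidney events are stopped at first occurrence (for liver, subject to footnote a), so those patients are normally not rechallenged.

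**Step 2: does the SAE sentence in Section 8.32 close the gap?** It would if every severe event were serious. Section 10.1 says otherwise: "A severe AE is NOT the same as a serious AE". A recurrent Grade 3 event that is not serious therefore falls outside the mandatory sentence and under the consultation sentence.

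**Step 3: compare the instructions.**

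| Case | Table 8.31, note or footnote | Section 8.32 | Result |
|---|---|---|---|
| A. Non-serious Grade 3 drug-related event, restart allowed, recurs at Grade 3 | Stop (note) | Consultation; may continue | Conflict |
| B. Same SAE, Grade 3 or severe, recurs at same or higher grade | Stop (note) | Stop | Agree |
| C. Grade 3 liver, infusion, lung or kidney event | Stop at first occurrence (liver subject to footnote a) | Normally not reached | Generally no conflict |
| D. Grade 2 AST/ALT/bilirubin unresolved at 12 weeks, asymptomatic, controlled, Investigator agrees | Discontinue (row) | May continue | Conflict |
| E. Other laboratory event in the all-other row, drug held at Grade 2, same conditions as D | Stop (footnote c) | May continue | Conflict |
| F. Grade 2 event at 12 weeks in these rows that is not a laboratory event, or is symptomatic | Discontinue | Stopping recommended | Same direction, different force |

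**Step 4: is there a tie-breaker?** Neither the note, the liver row nor footnote c points to Section 8.32, and Section 8.32 does not say that it overrides them. Where the table intends an exception it flags it in the row, as it does for Grade 3-4 liver events with footnote a. Section 8.32 also ties its longer dosing interval to recovery to Grade 0-1, so it gives no interval rule for a patient continued at Grade 2.

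**Step 5: does Section 8.0 settle it?** On the nominal calendar, Cycle 1 is 14 days and Cycle 2 is 21 days, so the strict period ends on day 14 + 21 = 35. Pembrolizumab starts on Cycle 2 Day 1, which is day 15. The earliest 12-week limit counted from a last dose is day 15 + 84 = 99. A 12-week decision therefore falls in the guidance period, and so, normally, does a recurrence on rechallenge. This bears on how binding the rules are. It does not say whether the table or Section 8.32 is the guidance to follow, and both keep mandatory wording.

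**Step 6: reach into the design.** Section 7.42 counts dose-limiting toxicities in Cycle 2 only, before these decisions normally arise. No alpha, power, sample size or decision boundary in Section 16 uses these rules.

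**The case against.** The strongest reply is that Section 8.32 is a specific exception placed after a general table, which is ordinary drafting. On the 12-week limit this is plausible: the section repeats the limit and then carves out a narrow laboratory case. It is fair to call that part a missing cross-reference. But no line states the exception, and the table's own practice is to mark exceptions in the row. The reply is weaker on recurrence, where the note covers any recurrent severe or Grade 3 drug-related event.

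A second reply is that continuing in the study might mean follow-up without pembrolizumab. This is arguable but not the natural reading. The laboratory sentence directly follows one about stopping study therapy, and the next paragraph is about patients who remain on therapy. The consultation sentence is contrasted with a mandatory stop of the drug.

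A third is that the liver row does not say permanently, unlike the Grade 3-4 row beneath it. That is correct, but Section 8.0 defines discontinuation as a complete stop.

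A fourth is that Section 8.0, and the title of Table 8.31, make all of this guidance. That softens the force of both texts. It does not reconcile them, and it adds a third reading.

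The objections on scope do stand. A reader might infer that every recurrent non-serious Grade 3 event is affected; the table normally removes the liver, infusion, lung and kidney events at first occurrence. A reader might infer that every laboratory event still at Grade 2 at 12 weeks is affected; Section 8.32 requires Investigator agreement, no symptoms and control. Footnote c belongs to the all-other row and to events for which drug was held, so it does not govern the liver row.

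**Conclusion.** Both conflicts are real, in limited form. The first covers recurrent Grade 3 or severe drug-related events that are not the same SAE at the same or a higher grade, in the five rows that allow restarting. The second is a strict clash only for asymptomatic, controlled laboratory events still at Grade 2 at 12 weeks with Investigator agreement; elsewhere the texts differ in force, not direction. The conclusion rests on reading continuation in Section 8.32 as continuation of pembrolizumab, and on the absence of any stated order of precedence.

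The size cannot be given. It is tempting to set one or two patients against the maximum of 38 (1/38 = 2.6%, 2/38 = 5.3%), but the documents supply no count or frequency for either situation. Nor do they support a claim that dose finding or the two-stage response design is compromised. MTD determination is essentially unaffected, and any effect on response, progression-free survival or the safety summaries runs through exposure and cannot be quantified. The case for correction is patient safety and uniform conduct across sites.

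**What to change.** Reconcile the note, the Grade 2 liver row and footnote c of Table 8.31 with Section 8.32, so that one rule remains for (1) a severe or Grade 3 drug-related event that recurs on rechallenge and (2) a laboratory event still at Grade 2 at 12 weeks. Put any intended exception in the row it modifies, or cross-reference it from there. State how the strict-then-guidance sentence in Section 8.0 applies to these stopping rules. Which rule stands is for the sponsor and the drug supplier to decide; this review takes no position. The cost is a wording amendment to Section 8, with no added procedures or patients.

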### 8.32 Other instructions for pembrolizumab

If pembrolizumab-related toxicity does not resolve to Grade 0-1 within 12 weeks after last administration of study drug, study therapy discontinuation is recommended. With Investigator agreement, patients with a laboratory adverse event still at Grade 2 may continue in the study only if asymptomatic and controlled.

In patients who continue on study therapy after experiencing an Adverse Event warranting potential dose modification, if considered drug-related by the investigator, once the patient has recovered to Grade 0-1 the dosing interval in

subsequent cycles will be increased by 1 week (e.g., to 3 weeks in patients who were on an every 2-week schedule). Following each such dose delay due to toxicity, the dosing interval should increase by an additional week. For example, patients who began the study on a 3-week dosing schedule, and have stopped drug twice for due to a drug-related toxicity that meets the above criteria, should now be dosing every 5 weeks.

For patients who experience a recurrence of the same severe AEs listed above with rechallenge of pembrolizumab, a consultation with the Investigator will occur to determine whether the patient should continue in the study. A patient who experiences the same SAE of the same NCI CTCAE grade or higher with rechallenge of pembrolizumab must discontinue pembrolizumab immediately.

Reduced dose of pembrolizumab dose (ie, below 200 mg) will not be administered.

## **9.0 Ancillary Treatment/Supportive Care**

### **9.1 Full supportive care**

Patients should receive full supportive care while on this study. This includes blood product support, antibiotic treatment, and treatment of other newly diagnosed or concurrent medical conditions. All blood products and concomitant medications such as antidiarrheals, analgesics, and/or antiemetics received from the first day of study treatment administration until 30 days after the final dose will be recorded in the medical records.

Suggested supportive care measures for the management of adverse events with potential immunologic etiology are outlined below. Where appropriate, these guidelines include the use of oral or intravenous treatment with corticosteroids as well as additional anti-inflammatory agents if symptoms do not improve with administration of corticosteroids. Note that several courses of steroid tapering may be necessary as symptoms may worsen when the steroid dose is decreased. For each disorder, attempts should be made to rule out other causes such as metastatic disease or bacterial or viral infection, which might require additional supportive care. The treatment guidelines are intended to be applied when the investigator determines the events to be related to pembrolizumab.

Note: if after the evaluation the event is determined not to be related, the investigator does not need to follow the treatment guidance (as outlined below). Refer to Section 8.2 for dose modification.

It may be necessary to perform conditional procedures such as bronchoscopy, endoscopy, or skin photography as part of evaluation of the event.

### **9.2 Blood products and growth factors**

Blood products and growth factors should be utilized as clinically warranted and following institutional policies and recommendations. The use of growth factors should follow published guidelines of the American Society of Clinical Oncology (ASCO) Update of Recommendations for the Use of White Blood Cell Growth Factors: An Evidence-Based Clinical Practice Guideline. *J Clin Oncol* 2006; 24:3187-3205, 2006.

#### **9.21 Neutropenia**

Prophylactic use of colony-stimulating factors including Granulocyte Colony-Stimulating Factor (G-CSF), pegylated G-CSF or Granulocyte Macrophage Colony-Stimulating Factor GM-CSF is not allowed in this study. Therapeutic use of G-CSF is allowed in patients with Grade 3-4 febrile neutropenia.

#### **9.22 Anemia**

Transfusions and/or erythropoietin may be utilized as clinically indicated for the treatment of anemia, but should be clearly noted as concurrent medications.

#### **9.23 Thrombocytopenia**

Transfusion of platelets may be used if clinically indicated. ITP should be ruled out before initiation of platelet transfusion.

### **9.3 Antiemetics**

Antiemetics may be used at the discretion of the attending physician. Nausea and vomiting should be treated aggressively, and consideration should be given to the administration of prophylactic antiemetic therapy according to standard institutional practice. Patients should be strongly encouraged to maintain liberal oral fluid intake. Volume depletion should be corrected before initiation of study drug.

**9.4 Anti-Diarrheals**

Patients should be monitored for signs and symptoms of enterocolitis (such as diarrhea, abdominal pain, blood or mucus in stool, with or without fever) and of bowel perforation (such as peritoneal signs and ileus). In symptomatic patients, infectious etiologies should be ruled out, and if symptoms are persistent and/or severe, endoscopic evaluation should be considered. (See Section 9.5 and 9.9a for management of treatment-related enterocolitis)

All patients who experience diarrhea should be advised to drink liberal quantities of clear fluids. If sufficient oral fluid intake is not feasible, fluid and electrolytes should be substituted via IV infusion.

NOTE: Loperamide/diphenoxylate/atropines should NOT be used for diarrhea symptoms unless: (1) it is believed that pembrolizumab-related enterocolitis is unlikely to be present after detailed evaluation by gastroenterology, including endoscopy; PLUS (2) approval is documented by a gastroenterology specialist.

**9.5 Management of treatment related enterocolitis**

In patients with severe enterocolitis, pembrolizumab will be held and treatment with systemic corticosteroids should be initiated at a dose of 1 to 2 mg/kg/day of prednisone or equivalent. When symptoms improve to Grade 1 or less, corticosteroid taper should be started and continued over at least 1 month.

In patients with moderate enterocolitis, pembrolizumab should be withheld and antidiarrheal treatment should be started. If symptoms are persistent for more than one week, systemic corticosteroids should be initiated (e.g., 0.5 mg/kg/day of prednisone or equivalent). When symptoms improve to Grade 1 or less, corticosteroid taper should be started and continued over at least 1 month.

**9.6 Anti-infectives**

Patients with a documented infectious complication should receive oral or IV antibiotics or other anti-infective agents as considered appropriate by the treating Investigator for a given infectious condition, according to standard institutional practice.

**9.7 Corticosteroids**

Patients requiring chronic steroid administration (excluding inhaled steroids) are excluded from the trial. Patients may continue on inhalation therapy. Corticosteroids are known immunosuppressive agents that can mitigate the effects of pembrolizumab. Steroids should be generally reserved to treat side effects of pembrolizumab. Steroids can be used as primary prevention of nausea per institutional guidelines, but steroid doses should be reduced in subsequent cycles if nausea/vomiting is absent or very mild (see Section 9.3).

**9.8 Concomitant medications**

Medications or vaccinations specifically prohibited in the exclusion criteria are not allowed during the ongoing trial. If there is a clinical indication for one of these or other medications or vaccinations specifically prohibited during the trial, discontinuation from trial therapy or vaccination may be required. The final decision on any supportive therapy or vaccination rests with the investigator and/or the subject's primary physician.

